6.3.6 Unscheduled Visit

If a subject return to the clinical site before their next scheduled visit for an assessment of an adverse event or at the request of the PI, all assessments completed at the Unscheduled Visit should be documented in the patient source record and in the eCRF.

6.4 LOST TO FOLLOW-UP

A participant will be considered lost to follow-up if he or she fails to return for ≥ 1 scheduled visits and is unable to be contacted by the study site staff.

The following actions must be taken if a participant fails to return to the clinic for a required study visit:

- The site will attempt to contact the participant and reschedule the missed visit within one week and counsel the participant on the importance of maintaining the assigned visit schedule and ascertain if the participant wishes to and/or should continue in the study.

- Before a participant is deemed lost to follow-up, the investigator or designee will make every effort to regain contact with the participant (where possible, 3 telephone calls and, if necessary, a certified letter to the participant's last known mailing address or local equivalent methods). These contact attempts should be documented in the participant's medical record or study file.
- Should the participant continue to be unreachable, he or she will be considered to have withdrawn from the study with a primary reason of lost to follow-up.]

7 STUDY ASSESSMENTS AND PROCEDURES

The following evaluations will be performed during the study outlined in the Schedule of Activities in Section 1.2.

7.1 INFORMED CONSENT PROCEDURES

The Principal Investigator(s) at each site will ensure that the subject is given full and adequate oral and written information about the nature, purpose, and possible risk and benefit of the study. Subjects must also be notified that they are free to discontinue from the study at any time. The subject should be given the opportunity to ask questions and allowed time to consider the information provided.

The subject's signed and dated informed consent must be obtained before conducting any study procedures.

The Principal Investigator(s) must maintain the original, signed Informed Consent Form. A copy of the signed Informed Consent Form must be given to the subject.

7.2 VITAL SIGNS

On injection visit, vital signs will be measured within 1 hour prior to dosing and within 30 minutes after dosing.

Vital signs will be measured before venipuncture. Vital signs include blood pressure (BP) and pulse measurements. After the patient has been sitting for 3 minutes, with back supported and both feet placed on the floor, systolic and diastolic BP will be measured using an automated validated device, with an appropriately sized cuff. In case the cuff sizes available are not large enough for the patient's arm circumference, a sphygmomanometer with an appropriately sized cuff may be used. If vital signs are out-of-range at screening/eligibility, the Investigator may obtain two additional readings, so that a total of up to three consecutive assessments are made, with the patient seated quietly for approximately five minutes preceding each repeat assessment. At least the last reading must be within the ranges provided above in order for the patient to qualify. All of the above tests will be performed after resting for 3 minutes at all visits.

Height in centimetres (cm) and body weight (to the nearest 0.1 kilogram [kg] in indoor clothing, but without shoes) will be measured at Visit 1 (Screening). Body mass index (BMI) will be calculated using the following formula: $BMI = \text{Body weight (kg)} / [\text{Height (m)}]^2$.

7.3 LABORATORY ANALYSIS OF BLOOD AND URINE

Collection of blood and urine will occur at the study site and the samples will be shipped to a central laboratory for analysis.

The following clinical labs will be performed:

Hematology

- Hemoglobin
- Hematocrit
- Red blood cell (RBC) count
- Platelet count
- White blood cell (WBC) count with differential

Chemistry

- Blood urea nitrogen (BUN)
- Creatinine
- Bilirubin (total, direct and indirect)
- Albumin
- Alkaline phosphatase (ALP)
- Aspartate aminotransferase (AST)
- Alanine aminotransferase (ALT)
- Creatine kinase
- Glucose
- Electrolytes (sodium, potassium, chloride, bicarbonate)

Urinalysis

- pH
- Specific gravity
- Protein
- Glucose
- Ketones
- Bilirubin
- Blood
- Nitrite
- Urobilinogen
- Leukocyte esterase

Other

- Human chorionic gonadotropin (HCG)^a
- Follicle-stimulating hormone (FSH)^b
- Luteinizing hormone (LH)^b

The Investigator must review the results of the Screening Visit clinical laboratory tests (including recheck results) and confirm that these results do not show evidence of any medical condition that would make study participation inappropriate. The Investigator should also assess any changes from baseline at the follow up visits and the Exit Visit.

Notes:

- a. Serum Pregnancy Test (i.e. HCG) will be performed for females of child bearing potential at screening only.
- b. FSH and LH will be performed for postmenopausal females at screening only.

7.4 URINE PREGNANCY TEST

Urine pregnancy test will be performed in WOCBP only as outlined in the Study Flow Chart in Section 1.2.

7.5 BEST-CORRECTED VISUAL ACUITY

Best-corrected visual acuity (including LL-BCVA) testing, performed by a certified VA examiner, should precede any examination requiring administration of eye drops to dilate the eye or any examination requiring contact with the eye. ETDRS best-corrected visual acuity (BCVA) will be obtained in each eye separately at screening (Visit 1). This assessment is to be performed prior to pupil dilation. The number of letters read correctly (for each eye) will be recorded in the appropriate study document. For the remainder of study visits (Visits 2-8), BCVA will only be obtained in the study eye.

7.6 COMPLETE OPHTHALMIC EXAM

The complete ophthalmic exam will consist of the following:

- External examination of the eye and adnexa.
- Routine screening for eyelids/pupil responsiveness (including ptosis, abnormal pupil shape, unequal pupils, abnormal reaction to light and afferent pupillary defect).
- Slit-lamp examination [cornea, anterior chamber, iris, lens, aqueous reaction (cells and flare). If an abnormal lens finding is noted during the slit-lamp examination, at any visit, then the finding should be further characterized with LOCS III. All subsequent visits for that subject should include LOCS III. A

complete description of LOCS III standardized procedures and grading scales is outlined in the MOP.

- Dilated fundus exam including evaluation of retina and vitreous (i.e. posterior segment abnormalities, retinal hemorrhage/detachment, and vitreal hemorrhage density and vitreous cells).
- Vitreal hemorrhage density and vitreous cells grading scales.
- Intraocular pressure (IOP) will be measured in both eyes at Visit 1 as per the study site's regular practice and recorded in the appropriate study document. For the remainder of study visits (Visits 2-9), IOP will only be obtained in the study eye.

7.7 OCULAR IMAGING

The following ocular images will be obtained as outlined in the visit schedule in Section 6.3. Also see Study Flow Charts in Section 1.2.

- Digital Color Fundus Photographs
- Fluorescein angiography
- Spectral Domain Optical coherence tomography
- Fundus Autofluorescence
- Infrared reflectance imaging. Only done at selected clinical sites with Heidelberg Spectralis® system.
-

7.8 POST-INJECTION ASSESSMENT

The study eye will be assessed before and after injection to ensure that the injection procedure and/or the study medication have not endangered the health of the eye. The initial post-injection assessment should be done within 15 minutes' post-injection and

include a gross assessment of vision (light perception) and monitoring IOP. If subject passes gross vision test and IOP is < 30mmHg, the subject may leave the site. If subject fails gross vision test and/or IOP is > 30 mmHg, assessments will continue every approximately 30 minutes until the subject passes gross vision test and IOP is < 30 mmHg.

Any subject who develops a significant and sustained raise in IOP (> 30 mmHg) or a non-adequately perfused central retinal artery (CRA) after injection, should be monitored according to the PI’s clinical judgment and may undergo additional procedures and measurements of IOP beyond those specified in the protocol as well as IOP lowering procedures. If any concern or immediate toxicity is noted, the subject will remain at the site and will be treated according to the PI’s clinical judgment.

7.9 BLOOD VOLUME FOR STUDY ASSESSMENTS

Blood volume during study (up to Day 150)

Assay	Number of Time Points	Approximate Volume per Time Point (mL)	Approximate Sample Volume Over Course of Study (mL)
Pharmacokinetics	4/9	4	36
Haematology	5/9	4	36
Chemistry (Incl. HCG/LH/FSH)	5/9	8.5	76.5

Total Blood Volume for Study 148.5 mL

7.10 ADVERSE EVENTS AND SERIOUS ADVERSE EVENTS

All adverse events (AEs) (as defined in Section 7.9.1), either observed by the PI or one of their medical collaborators, or reported by the participant spontaneously, or in response to direct questioning, will be reported. All adverse events (ocular, non-ocular, serious, non-serious, volunteered, and elicited) must be documented in study records.

7.10.1 DEFINITION OF ADVERSE EVENTS (AE)

An adverse event is any untoward medical occurrence in a subject who receives a pharmaceutical product. The occurrence does not necessarily have to have a causal relationship with the treatment. Therefore, an AE can be any unfavorable and unintended sign, symptom, or disease temporally associated with the use of a drug, whether or not considered related to the drug.

Note:

- For purposes of this study, abnormal laboratory values will not be considered adverse events unless deemed clinically significant by the Investigator. All abnormal laboratory values will be recorded in the database and appropriate analyses presented in the final study report.

7.10.2 DEFINITION OF SERIOUS ADVERSE EVENTS (SAE)

A serious adverse event (SAE) is defined as any untoward medical occurrence that at any dose:

- Results in death;

- Is life-threatening: this means that the subject was at risk of death at the time of the event; it does not mean that the event might have caused death had it occurred in a more severe form;
- Required hospitalization or prolongation of existing hospitalization;
- Results in persistent or significant incapacity or substantial disruption of the ability to conduct normal life functions; or
- Is a congenital anomaly or birth defect.

Important medical events that may not result in death, be life-threatening, or require hospitalization may be considered serious when, based upon appropriate medical judgment, they may jeopardize the patient or subject and may require medical or surgical intervention to prevent one of the outcomes listed in the above definition.

Medical and scientific judgment should be exercised in deciding if an AE is serious and if expedited reporting is appropriate

7.10.3 ADVERSE EVENTS OF SPECIAL INTEREST

An adverse event of special interest is one of scientific and medical concern specific to the Sponsor's product or program where ongoing monitoring and rapid communication by the Investigator to the Sponsor may be appropriate. These adverse events may be serious or non-serious. Applicable adverse events may require further investigation in order to characterize and understand, and depending upon the nature of the event, rapid communication by the trial Sponsor to other parties may also be required. These adverse events of special interest must be reported using the same mechanism and timeframe (i.e. within one working day of the Investigator's or delegate's knowledge of the event) as described for serious adverse events in Section 7.9.2. The adverse events of special interest include the following:

- Endophthalmitis
- 4+ ocular inflammation

- 2-3+ ocular inflammation that fails to decrease to 1+ or less within 30 days of the onset of the event
- Sustained (> 5 minutes) loss of light perception after FCA injection
- Sustained elevation of IOP (30 mmHg) at/past 90 minutes' post-injection
- Any elevation of IOP requiring surgical intervention (i.e. paracentesis)
- New vitreous hemorrhage of > 2+ severity that does not resolve within 14 days of the onset of the event
- Cataract progression

If an adverse event of special interest occurs in a study subject, the study subject will be followed for resolution of the adverse event. A decision will be made by the Sponsor concerning further exposure to the study treatment and further participation in the study.

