 - a. Women of non-childbearing potential (WONCBP), or
 - b. Women of childbearing potential (WOCBP) with a negative pregnancy test at screening and must agree to use protocol defined methods of contraception for the duration of the study.
 7. Males with female partners of childbearing potential must agree to use protocol defined methods of contraception and agree to refrain from donating sperm for the duration of the study.
 8. Willing and able to give informed consent.

Note: If both eyes meet the inclusion criteria, the eye with the best visual acuity at the screening visit will be designated as

the study eye. If both eyes have the same visual acuity, the right eye will be used as the study eye.

Exclusion Criteria: Unless specified otherwise, ocular specific exclusion criteria apply to the study eye only.

1. GA due to causes other than AMD such as Stargardt disease, cone rod dystrophy or toxic maculopathies like plaquenil maculopathy.
2. Spherical equivalent of the refractive error demonstrating > 6 dioptres of myopia or an axial length of >26 mm.
3. Evidence of exudative (wet) AMD including evidence of retinal pigment epithelium rips or evidence of neovascularization anywhere in the retina based on fluorescein angiogram as assessed by the PI in either eye within 12 months.
4. Retinal disease likely to confound visual performance or be affected by intraocular steroid.
5. Any ophthalmologic condition that reduces clarity of the media and that, in the opinion of the investigator interferes with ophthalmologic examination (e.g. advanced cataract or corneal abnormalities).
6. Any ophthalmologic condition that prevents adequate imaging of the retina judged by the PI.
7. Intraocular surgery (including lens replacement surgery) within 3 months prior to dosing.
8. Aphakia or absence of the posterior capsule. Previous violation of the posterior capsule is also excluded unless it occurred as a result of yttrium aluminum garnet (YAG) laser posterior capsulotomy in association with prior

posterior chamber intraocular lens implantation and at least 60 days prior to Day 0.

9. Any ophthalmologic condition that may require surgery during the study period.
10. Glaucoma or family history of glaucoma.
11. Any contraindication of IVT injection including current ocular or periocular infection.
12. History of uveitis or endophthalmitis.
13. History of choroidal neovascularization (CNV) in either eye.
14. History of IVT injection of steroids within 12 months.

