The presence of drusen and pigmentary abnormalities in the central macula is the main ocular risk factor for late age-related macular degeneration. The greater the area of drusen at the macula the greater the risk of progression to loss of vision. Using the direct ophthalmoscope or a slit lamp these early changes can be detected.

AMD is a highly complex disease that is affected by multiple factors, such as ageing, genetic predisposition, environmental elements, oxidative stress and inflammatory effects [2, 5, 6]. Smoking, age, alcohol consumption, diet and obesity are important risk factors related to oxidative stress [6, 7]. High body mass index, cardiovascular disease, hypertension and a variety of dietary patterns are risk factors less consistently[8]. Several single-nucleotide polymorphisms (SNPs) that confer increased or decreased risk of inflammation have been identified. They include the well-recognized *complement factor H* (CFH), *CX3CR1*, *Toll-like receptor 3* (TLR3), TLR4, and *interleukin 8* (IL-8)[9]. Although AMD is not a classic inflammatory disease, inflammatory cells have an important role in AMD pathogenesis and progression [5, 10, 11]. Evidence has also suggested that some infectious agents are associated with AMD.

Although relatively simple to diagnose through direct visualization augmented with rapid sequence fluorescein angiography, treatment has presented a far greater challenge because the true etiology of AMD is largely unknown [12]. Within the past decade, researchers have introduced many new, potentially promising treatment and prevention

options in an attempt to minimize the damage imparted from AMD. The current standard-of-care for the treatment of exudative AMD are the anti-VEGF agents, such as ranibizumab (Lucentis®), aflibercept (Eylea®) and off-label bevacizumab (Avastin®) [13]. No therapy exists for GA which is usually bilateral and relentlessly progressive. Dexamethasone and triamcinolone acetonide (TA) are the commonly used corticosteroids for macular oedema [14, 15]. Most studies showed their effectiveness in improving vision function and reducing macular oedema. Nevertheless, intravitreal injection of corticosteroids carries significant complication risk such as cataract progression, ocular hypertension and endophthalmitis.

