5.2 TREATMENTS ADMINISTERED

5.2.1 DOSE LEVELS AND STUDY ARMS

A single dose of 1- and 2 mg Fludrocortisone acetate/0.1mL will be tested in this study. Subjects will receive 1 IVT injection as outlined in the table below.

	Treatment Arm	Dose Escalation
Part 1	Fludrocortisone acetate 1 mg/0.1mL at Day 0	If no dose limiting toxicity is observed in 3 patients at this given dose level, the dose will be escalated to the following level:
Part 2	Fludrocortisone acetate 2 mg/0.1mL at Day 0	

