6.2 SUBJECT ENROLLMENT

It is the responsibility of the investigator to ensure that subjects are eligible to participate in the study prior to enrollment and throughout the study. Documentation of the personally signed and dated informed consent of each subject, using the study-specific ICF, is required before initiating the Screening process. After written informed consent has been obtained and eligibility to participate established, investigative site personnel will obtain the subject's identification number. Only eligible subjects will be allocated to the open label FCA 1 mg/0.1mL or 2mg/0.1 mL.

Enrollment will occur in two parts in order to minimise the likelihood that subjects will be exposed to risks. During part 1 & 2, subjects will be screened one by one as only one patient will initially be enrolled during part 1 of the trial. The first enrolled subject will participate in a screening period of up to 14 days and a follow-up period of 28 days, to detect an IOP response.

After first subject has completed the follow-up of 28 days after FCA 1mg/0.1 mL injection, The subject's safety data will be reviewed the safety data of this will be reviewed by an independent safety review committee to determine whether to commence enrolment of additional 2 patients in the first cohort of 1mg/0.1mL dose of FCA. Enrolment will be stopped if >2 patients experience limiting-toxicity adverse event related to the study drug. If no more than two adverse events considered to be related to the study drug occur with limiting toxicity, the second cohort will be recruited. Dose-limiting toxicity is defined by intraocular inflammation, elevated IOP, reduced vision (loss of ≥ 15 letters), or haemorrhage within 28 days after injection.

Part 2 will take in place if the 3 subjects have tolerated well the dose. Part 2 initially involves a single subject treated with 2mg/0.1mL FCA to assess safety and tolerability. This subject will be followed for up to 28 days and reviewed by an independent safety

review committee prior to the recruitment of a further 5 subjects treated with 2mg/0.1mL FCA totalling in 6 subjects in the second cohort.

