Meeting minutes will be generated at each meeting and included in the sponsor's study files. Formal reports will not be prepared prior to or following these meetings. As general guidance, a subject will be considered to have tolerated a dose if the subject experiences no clinically significant drug-related adverse event or laboratory abnormality. Conversely, a subject will not be considered to have tolerated the dose if he experiences a clinically significant drug-related adverse event or laboratory abnormality during the study drug administration or post-administration follow-up period.

Safety to cataract will be reviewed among all participants at the 150 day review.

It is understood that safety is a medical judgment that cannot be prospectively defined in detail. Subjects will be closely monitored with clinical observations and safety laboratory testing.

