7.11 EXPECTED ADVERSE EVENTS

7.11.1 EXPECTED AE RELATED TO THE TEST ARTICLE

No ocular or systemic AE related to the investigational drug are expected at the doses proposed in this protocol.

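### In a single-injection trial, the AESI clause in 7.10.3 and the eligibility duty in 6.2 allow a dosed participant to be taken out of observation because of toxicity

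*Protocol*

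**What the plan says.** - **Dosing.** Protocol 5.2.1: "Subjects will receive 1 IVT injection as outlined in the table below". The injection is given on Day 0, and the schedule of activities (1.2) then runs to Day 150.
- **After an AESI.** Section 7.10.3 lists endophthalmitis, defined grades of ocular inflammation, sustained loss of light perception, sustained or surgically treated pressure elevation, persistent vitreous haemorrhage and cataract progression. It follows the event to resolution and then adds: "A decision will be made by the Sponsor concerning further exposure to the study treatment and further participation in the study". It gives no criteria for that decision.
- **Eligibility.** Section 6.2 requires the investigator to "ensure that subjects are eligible to participate in the study prior to enrollment and throughout the study".
- **Exclusion criteria (1.1).** These include "History of uveitis or endophthalmitis" (criterion 12), "Glaucoma or family history of glaucoma" (criterion 10) and, under criterion 9, an eye condition that may need surgery while the study is running.
- **Day 150.** Section 6.2 also plans: "Safety to cataract will be reviewed among all participants at the 150 day review".
- **Analysis.** The Safety Population is everyone dosed (8.1). ITT in 8.1 needs a visit at or after month 2, and per protocol needs Day 150. Missing data are generally not imputed (8.7).

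**The concern.** Stopping rules for participation normally serve to stop further dosing. Here none is left after Day 0, so ending participation protects nobody from exposure and only ends data collection. The two rules tie that step to safety outcomes, directly in 7.10.3 and indirectly through the eligibility duty in 6.2.

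If a participant left for that reason, the data lost would be informative: later events, and visual acuity, pressure, lens and atrophy size at Days 60, 90 and 150. The by-visit summaries for those days would then lean towards participants without complications. Dose-limiting toxicity covers only the first 28 days, so evidence on later toxicity, cataract above all, depends on these visits. In an open-label study, the choice would also rest with the Sponsor.

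**Working it through.** The protocol states no power, dropout or AESI rate, so there is no figure to reproduce. The check compares the texts and then shows what losing one participant does.

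**1. Is there any exposure to decide on?** Section 5.2.1 gives one injection and 7.10.3 provides for a decision on more. After Day 0 the number of planned doses is 0, so only the participation half of the sentence can have an effect.

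**2. Can toxicity make a dosed participant ineligible?**

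| On-study event | Named as a risk or AESI | Exclusion criterion it could match |
|---|---|---|
| Endophthalmitis | 2.2 and 7.10.3 | 12 |
| Ocular inflammation | 7.10.3 | 12, if diagnosed as uveitis |
| Raised pressure | 2.2 and 7.10.3 | 10, if diagnosed as glaucoma; 9, if surgery may be needed |
| Cataract progression | 2.2 and 7.10.3 | 9, if surgery may be needed |

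Section 2.2 supports the link: "intravitreal injection of corticosteroids carries significant complication risk such as cataract progression, ocular hypertension and endophthalmitis". Read literally, an eligibility duty lasting the whole study is breached by these events.

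**3. Does anything hold such a participant in follow-up to Day 150?** Section 7.10.3 follows the AESI to resolution, and 7.10.5 follows SAEs until the acute event resolves, even after discontinuation. Neither secures the remaining scheduled visits. Section 7.11.3.1 offers an early termination visit to participants who wish to withdraw and does not mention participation ended by the Sponsor. An early visit also cannot show Day 150 status.

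**4. Weight of one participant.** Cohorts are 3 (1 mg) and 6 (2 mg), from 1.1.
- 1/3 = 33%; 1/6 = 17%; overall 1/9 = 11%.

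**5. Illustration at Day 150, 2 mg cohort (hypothetical).** One of six is affected and is removed before Day 150.
- Proportion affected, everyone seen: 1/6 = 17% (exact 95% CI 0.4% to 64%).
- After removal: 0/5 = 0% (exact 95% CI 0% to 52%).
- Mean acuity change, with one 15-letter loss and five unchanged: (−15 + 5 × 0)/6 = −2.5 letters. After removal: 0/5 = 0 letters.

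These concern status at the visit, not AE incidence.

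**6. How often could the clause come into play?** The per-participant AESI rate p is an assumption, varied from 5% to 30%. The chance of at least one AESI is 1 − (1 − p)^n.

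| p | n = 6 | n = 9 |
|---|---|---|
| 5% | 26.5% | 37% |
| 10% | 47% | 61% |
| 20% | 74% | 87% |
| 30% | 88% | 96% |

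This is the chance that the Sponsor's decision arises, not the chance that anyone is removed.

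**7. Analysis sets.** Under 8.1, a participant removed before month 2 leaves ITT, and one removed before Day 150 leaves per protocol. The Synopsis defines ITT by any post-dose efficacy measurement, so under that definition an early removal would usually stay in ITT. The Safety Population is unaffected under either.

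**The case against.** The strongest reply is that the protocol nowhere directs removal, and this stands. No section says that a dosed participant who later meets an exclusion criterion is withdrawn, and 7.10.3 leaves a decision open. Several sections assume that affected participants continue. Section 7.6 applies LOCS III grading at all visits after an abnormal lens finding, 7.8 answers raised pressure with extra monitoring, and 5.3.1 leaves endophthalmitis treatment to the investigator without mentioning withdrawal. Eligibility is verified at baseline before injection (6.3.2), and several criteria are anchored to dosing, so they read most naturally as entry criteria.

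A reader might also infer that toxicity would disappear from the safety results. The documents do not support that. The triggering event stays in the treatment-emergent AE summary (8.3), its denominator is everyone dosed (8.1), the event is followed to resolution, and an independent DSMB reviews cumulative safety (9.7). Nor is there good ground to say that escalation is distorted. The dose-limiting window is 28 days, and most AESIs inside it would themselves be dose-limiting.

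Two further limits apply. New hypertension and choroidal neovascularisation match exclusion criteria but are not AESIs, so the Sponsor clause does not reach them. And these events should not be called expected toxicities, since 7.11.1 says: "No ocular or systemic AE related to the investigational drug are expected at the doses proposed in this protocol". They are events listed as AESIs or named as class risks.

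What remains is that the participation clause and the eligibility duty are both in force, neither has limits, and no rule keeps a dosed participant in scheduled visits. The sections that point towards continued follow-up show what was probably meant. They do not override the text.

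**Conclusion.** The point holds as a defect of wording with a real but bounded consequence. The protocol permits, and does not require, ending observation of a dosed participant because of toxicity. The AE that prompts it would still be counted and followed. At risk are later events and the Day 60 to 150 acuity, pressure, lens and atrophy data, lost in a way that depends on the outcome, and the completeness of the planned Day 150 cataract review.

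One such loss takes away 33% of the 1 mg cohort or 17% of the 2 mg cohort, with generally no imputation. The change from 1/6 to 0/5 and from −2.5 to 0 letters assumes that one affected participant is removed and has no Day 150 assessment. The documents give neither an AESI rate nor a removal rate, so the size shows how sensitive the summaries are and is not a forecast. The change is worth making because it is cheap and because durability of safety is what the later visits are for.

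**What to change.** 1. **Section 7.10.3.** Replace the whole last sentence, since deleting only part of it leaves a fragment. Reconcile it with the single-dose design and do not make continued observation a Sponsor decision after an AESI. Possible text: *A participant who has an adverse event of special interest continues scheduled data collection to Day 150 unless consent is withdrawn. The investigator may omit an individual procedure on medical grounds and records the reason.*
2. **Section 6.2.** Limit the investigator's eligibility duty to the period up to dosing on Day 0.
3. **Section 6.2 or 7.11.3.1.** State that meeting an exclusion criterion or having an AE after dosing does not by itself end scheduled data collection to Day 150. Care of the event stays with the investigator's medical judgement.

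**Cost.** A few sentences in a protocol amendment. No visits are added, because the schedule already runs to Day 150. The one downside is that participants with complications keep their scheduled visits, which the allowance to omit individual procedures eases.
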